9.2.1.1 Site(s) Performing Correlative Study

The primary endpoints (IHC for CD8 and CD3) will be evaluated on FFPE slides of tumor tissue at Phenopath Laboratories, Seattle, WA. All other IHC will be performed at the University of Virginia.

9.2.2 Gene Expression Analyses of Tumor Biopsies, Fine Needle Aspirates of Metastases, and Peripheral Blood—Laboratory Correlative Study #2

Tumor biopsies will be obtained as described above for IHC analyses. FNA of melanoma metastases will be performed at each biopsy date, before the excisional/incisional/core biopsy; both tissues will be evaluated for gene signatures. Gene signatures will also be performed on PBMCs obtained before therapy and on days 21 and 42, the same day of the tumor biopsies. PBMC gene signatures may be compared to data of tumor biopsy, immunologic response, and clinical response.

9.2.2.1 Collection of Specimen(s)

For FNA a 22- or 23-gauge hypodermic needle will be inserted into the tumor and multiple passes with changing angles of insertion will be made through all quadrants of the tumor, while under suction. Tissue from the needle will be suspended in 10 mL of cold RPMI. For PBMC, a CPT tube will be drawn and processed as described below.

9.2.2.2 Handling of Specimen(s)

Specimens will be collected at the clinical sites as described above and centrifuged at 1500 rpm for 5 minutes at 4°C. The cell pellet will then be harvested, red blood cells lysed as per the technique described by Weiss et al [[Weiss 2011](#)]. Cells will be isolated by centrifugation and resuspended in Qiazol to obtain total RNA. Samples will be stored at -80°C and then batch-shipped as described below.

9.2.2.3 Shipping of Specimen(s)

All RNA samples will be batched and shipped on dry ice using FedEx® overnight delivery to the CITN Central Laboratory. The CITN Central Laboratory will hold specimens for shipment to the laboratory of [name] and [name] for gene expression array studies. Any leftover sample will be returned to the CITN Central Laboratory for storage and future ancillary studies.

9.2.2.4 Site(s) Performing Correlative Study

Gene expression studies, including analyses of the data, will be conducted in the laboratory of [name], Chief Research Officer of Sidra Medical and Research Center, Qatar.

9.2.3 CD8+ T-cell IFN-gamma Responses to the 12-peptide Mixture, and CD4+ T-cell Responses to Tetanus Peptide—Laboratory Correlative Study #3

PBMC (and lymphocytes isolated from tumor biopsies, when available) will be analyzed by IFN-gamma ELISpot assay for responses to the 12-peptide mixture. Assessment of immunologic response will be based on a fold-increase measure from baseline as well as using a positivity threshold. Since 11 of the 12 melanoma-associated immunizing peptides are 9- and 10-mers, it is safely presumed that IFN-gamma ELISpot responses among PBMC will derive from CD8⁺ T cells. No depletion of CD4⁺ T cells is planned for the ELISpot testing. The frequency of CD8+ T cells specific to 8 of the 12 immunizing peptides will be confirmed using tetramers and flow cytometric analysis. CD8+ T cell

responses will be assayed directly ex vivo (using viably cryopreserved specimens), after stimulation with the 12-peptide mixture (10 µg/mL each) at baseline (i.e., before initiating INCB024360 treatment), at week 3 (before the first immunization with MELITAC12.1), at weeks 6, and optionally at week 16 (2 weeks after the last dose of MELITAC12.1).

Similarly, these assays will include the tetanus peptide and multiple controls (CEF peptide, negative controls, etc.). Responses to the tetanus peptide will be interpreted as helper (CD4+) T-cell responses.

9.2.3.1 Collection of Specimen(s)

Whole blood will be collected into heparinized (green top) tubes.

9.2.3.2 Handling of Specimen(s)

Samples will be collected at room temperature and shipped to the CITN Central Laboratory the same day as the blood draw, so that the sample is received at the central laboratory within 24 hours of blood draw. PBMC will be isolated and cryopreserved before testing.

9.2.3.3 Shipping of Specimen(s)

Samples will be shipped at ambient temperature for overnight FedEx delivery. Clinical research sites will utilize a web-based specimen tracking system (BSI-II) to communicate with the CITN central laboratory.

9.2.3.4 Site(s) Performing Correlative Study

The IFN-gamma ELISpot assay will be conducted at the CITN Central Laboratory at the University of Washington Immunologic Monitoring Laboratory in Seattle, in collaboration with the laboratory of [name] at the University of Virginia. Flow cytometry for tetramer-positive cells will be conducted in the laboratory of [name].

9.2.4 Quantification of PBMC and T-cell Subsets—Laboratory Correlative Study #4

The effect of treatment on T lymphocyte number and phenotype (i.e., CD8+, effector memory CD8+, central memory CD8+, CD4+, CD4+ Treg, naïve subsets) will be assessed. The frequency and percentage of PBMC subsets will be determined using multiparameter flow cytometric analysis of whole blood. The markers include CD3, CD8, CD4, CD39, CD56, Foxp3, CD127, CD45RA, CD45RO, CCR7, CD28, CD27, CD25, CD122, CD86, CD14, CD16, CD19, CD123, and CD11c. Changes in myeloid-derived suppressor cell populations will also be assessed by flow cytometry.

The effect of INCB024360 and MELITAC 12.1 on lymphocyte number and phenotype will be assessed at baseline (i.e., before initiating INCB024360 treatment), week 3 (before first immunization with MELITAC12.1), week 6 (before the second set of MELITAC12.1 vaccines), week 14 (just before the last dose of MELITAC12.1), and, if possible, week 16 (2 weeks after the last dose of MELITAC12.1).

9.2.4.1 Collection of Specimen(s)

Whole blood will be collected into heparinized tubes.

9.2.4.2 Handling of Specimen(s)

Samples will be collected at room temperature and shipped to the CITN Central Laboratory the same day as the blood draw, so that the sample is received at the central laboratory within 24 hours of blood draw.

9.2.4.3 Shipping of Specimen(s)

Samples will be shipped at ambient temperature for overnight FedEx delivery. Clinical research sites will utilize a web-based specimen tracking system (BSI-II) to communicate with the CITN central laboratory.

9.2.4.4 Sites Performing Correlative Study

The immunophenotyping assays will be conducted at the CITN Central Laboratory.

9.2.5 Intratumor and Whole Blood Kyn/Trp Ratios—Laboratory Correlative Study #5

Kyn/Trp ratios will be assayed in patients receiving a regimen of INCB024360 plus MELITAC 12.1 vaccine as measured in peripheral blood and in intra-tumoral specimens at baseline and on specimens obtained at subsequent tumor biopsy timepoints.

Evaluations will occur at baseline (week 0) and after each vaccination.

9.2.5.1 Collection of Specimens

Whole blood will be collected into heparinized tubes.

Biopsy specimens will be collected as described in [Section 9.1.1](#)

9.2.5.2 Handling of Specimen(s)

Blood samples will be processed locally, and frozen aliquots shipped to the CITN Central Laboratory. The Central Laboratory will distribute aliquots to Incyte where testing will be done in a blinded fashion.

Biopsy specimens will be collected and stored at -80°C (if frozen) at the collection site.

9.2.5.3 Shipping of Specimens

Frozen plasma and flash frozen biopsy specimens will be batch shipped to the CITN Central Laboratory. The CITN Central Laboratory will ship specimens to Incyte Corporation by FedEx overnight delivery.

9.2.5.4 Site(s) Performing Correlative Study

The Kyn/Trp analysis will be conducted at Incyte Corporation.

9.2.6 Other Immunologic Assessments—Laboratory Correlative Study #6

9.2.6.1 Collection of Specimens

At baseline, week 3, week 6 and optionally at week 16, 10 mL of serum will be collected in red-top tubes for serum storage, and 10 mL will be collected in green-top tubes for plasma storage.

9.2.6.2 Handling of Specimen(s)

Samples will be collected at room temperature. Blood for serum, plasma, and the cell pellet into RNA will be processed at the Local Lab within 4 hours at the collection site, aliquoted according to protocol, and frozen at -80°C.

9.2.6.3 Shipping of Specimen(s)

Serum, plasma and cell pellet into RNA will be processed at each clinical site and batch-shipped on dry ice overnight to the CITN central laboratory. Clinical research sites will utilize a web-based specimen tracking system (BSI-II) to communicate with the CITN central laboratory. Frozen samples will be batch-shipped to the CITN central laboratory/repository on dry ice.

9.2.6.4 Site(s) Performing Correlative Study

It is anticipated that a number of CITN investigators with laboratories may propose ancillary studies to be conducted on CITN repository specimens, but the specific sites have yet to be determined.

9.3 Special Studies: Cytokine and INCB024360 Blood Levels

9.3.1 Collection of Specimens

10 mL of serum will be collected in red-top tubes for determining the INCB024360 level, and cytokine levels.

9.3.2 Handling of Specimen(s)

Samples will be collected at room temperature and processed in the local laboratory within 4 hours of blood draw, aliquoted according to protocol, and frozen at -80°C.

9.3.3 Shipping of Specimen(s)

Frozen aliquots of serum and plasma will be batch-shipped to the CITN Central Laboratory. The Central Laboratory will distribute aliquots to Incyte. Clinical research sites will utilize a web-based specimen tracking system (BSI-II) to communicate with the CITN Central Laboratory.

9.3.4 Site(s) Performing Correlative Study

The INCB024360 drug levels will be conducted at Incyte Corporation.

10. STUDY CALENDAR

All baseline evaluations are to be conducted within 1 week before start of protocol therapy. Scans and x-rays must be done \leq 4 weeks before the start of therapy. In the event that the patient's condition is deteriorating, laboratory evaluations should be repeated within 48 hours before initiating the next cycle of therapy.

	Pre-Study -30 day	Pre-Study -7 day	Wk 0 Day 0	Wk 1 Day 7 +/- 2 d	Wk 2 Day 14 +/- 2d	Wk 3 Day 21 +/- 2d	Wk 4 Day 28 +/- 2d	Wk 5 Day 35 +/- 2d	Wk 6 Day 42 +/- 2d	Wk 8 Day 56 +/- 2d	Wk 11 Day 77 +/- 2d	Wk 14 Day 98 +/- 2d	Wk 16 Day 112 +/- 2d	Repeat ^b Cycles Wks ^c +/-2d	10 Wk Post-Tx F/U ^d F/U +/-14d	36 Wk Post-Tx FU F/U +/-30d	Off Study
INCB024360 daily			X	X	X	X	X	X	X	X	X	X	X	→	X		
MELITAC 12.1 vaccine**						X	X	X		X	X	X					
Informed consent	X																
Demographics	X																
Medical history	X																
Concomitant medication		X	X	X	X	X	X	X	X	X	X	X	X	X	X	X	X
Physical exam		X	X			X		X		X	X	X	X	X	X	X	X
Vital signs		X	X	X	X	X	X	X	X	X	X	X	X	X	X	X	X
Height		X													X		
Weight		X	X	X	X	X	X	X	X	X	X	X	X	X	X	X	X
Performance status		X	X	X	X	X	X	X	X	X	X	X	X	X	X	X	X
Tumor Biopsy ^{1,2*}			X ^a			X			X ³				X ³				X ¹
FNA ^{4,5}			X ^a			X			X				X ³				X ¹
CBC w/diff, plts (local lab)		X	X	X	X	X	X	X	X	X	X	X	X	X	X	X	X
Serum chemistry ⁶ (local lab)		X	X	X	X	X	X	X	X	X	X	X	X	X	X	X	X
B-HCG ⁷ (local lab)			X ⁷														
PBMC ⁵ and T-cell subsets			X			X			X			X	X ⁸				
IFN-gamma ELISpot***			X			X			X			X	X				
Confirmatory Tetramer staining			X			X			X			X					

	Pre-Study -30 day	Pre-Study -7 day	Wk 0 Day 0	Wk 1 Day 7 +/- 2 d	Wk 2 Day 14 +/- 2d	Wk 3 Day 21 +/- 2d	Wk 4 Day 28 +/- 2d	Wk 5 Day 35 +/- 2d	Wk 6 Day 42 +/- 2d	Wk 8 Day 56 +/- 2d	Wk 11 Day 77 +/- 2d	Wk 14 Day 98 +/- 2d	Wk 16 Day 112 +/- 2d	Repeat ^b Cycles Wks ^c +/-2d	10 Wk Post-Tx F/U [‡] F/U +/-14d	36 Wk Post-Tx FU F/U +/-30d	Off Study
Kyn/Trp ratio			X			X			X					X*			
RNA Cell Pellet for gene expression analysis			X			X			X					X			
Serum Cytokines			X			X			X					X			
INCB024360 level						X			X					X			
Circulating tumor cells			X											X			
PBMC storage***			X			X			X					X ⁸	X		
Serum storage			X			X			X					X ⁸			
EKG (pre-study and as indicated)	X																
Adverse event evaluation	X	X	X	X	X	X	X	X	X	X	X	X	X		X	X	X
Tumor measurements	X			Tumor measurements are repeated every 12 weeks or per institutional standard of care. Documentation (radiologic) must be provided for patients removed from study for progressive disease.													
Radiologic evaluation ⁹	X		.											X ⁹			X ⁹

^aTumor biopsy and FNA may be obtained up to 14 days prior to starting therapy. For patients with only one or two tumors approachable for biopsy, available tumor blocks from prior biopsies can serve as the pretreatment sample provided at least 20 unstained slides are available.

^bPatients who are eligible to receive additional cycles of IDO inhibitor without vaccinations will maintain the same visit schedule as cycle 1

NOTE: If additional cycles of IDO inhibitor are given only the end of treatment biopsy is to be obtained when possible.

Note: If additional cycles of IDO inhibitor are given a reduced volume of blood will be drawn for correlative assays. See footnote *** below for details.

^cA delay of up to 60 days between treatment cycles will be allowed.

¹Tumor biopsies will be assessed by immunohistochemistry (IHC)

²If optional biopsy performed

³Optional biopsy

⁴FNA (Fine Needle Aspirate): before the excisional/incisional/core biopsy

⁵Gene Expression Analyses of tumor biopsies, FNA, and PBMC

⁶Serum chemistries include: albumin, alkaline phosphatase, total bilirubin, bicarbonate, BUN, calcium, chloride, creatinine, glucose, phosphorus, potassium, total protein, SGOT [AST], SGPT [ALT], sodium.

⁷Serum Pregnancy test done 48 hours before start of therapy

⁸Optional blood draw

⁹CT, MRI, or PET within 0 days (14 days preferred) is acceptable for imaging assessment purposes

⁹ Radiologic evaluations done at weeks 8 and 16 +/- 7 days. If a clinical response is seen at week 8 a confirmatory scan is to be repeated at least 4 weeks later (week 12), therefore the week 16 scan can be delayed an additional 4 weeks and repeated at week 20. After week 26 scans are to be done every 12 weeks in patients without progression through year 5 of follow-up.

* Pretreatment biopsies should be performed before the first treatment with IDO inhibitor, within 14 days of that start date.

**A participant will be taken off protocol treatment if >1 vaccination is delayed [\pm 3 to 7 days] during the treatment period.

***For cycles beyond cycle 1, correlative science blood draws will be limited to only IFN-gamma ELISpot/PBMC Storage.

11. MEASUREMENT OF EFFECT

In all patients, assessments for toxicology, response, and pharmacodynamics for immunologic effect will be performed. Effects of IDO inhibition on systemic vaccine-induced immunity will be assessed by evaluating peripheral blood immune responses to the MELITAC 12.1 vaccine. The comparator for immune responses will be published experience with similar patients treated with the same vaccine regimen but without INCB024360 [[[name], 2011](#); [[name] 2009](#)]. If substantial changes at sites of tumor are detected in response to INCB024360 alone or in combination with vaccine, subsequent iterative trials will determine the individual contributions of INCB024360 and the vaccine. From these data, we will endeavor to associate any observed changes with the expression of IDO1 protein by IHC in tumor or tumor-infiltrating cells.

The primary endpoint will be changes in the concentration and number of CD8+ cells infiltrating tumor before and after treatment with each patient serving as their own control. We will use the assessment of total CD3 T cells and total CD45 lymphocytes as confirmatory assays. The histologic pattern of T-cell infiltration and changes in pattern will be concurrently assessed and chronicled. Whether to expect a small or large effect on the tumor microenvironment from the therapy remains unknown, thus the endpoint objectives are exploratory and the trial is sized accordingly. A prior study of changes in the tumor microenvironment with systemic immune therapy (IL-2) identified significant changes in the tumor microenvironment with a sample size of 13 patients. The sample size of 12 patients is a reasonable number for this initial study to determine whether INCB024360 plus vaccine has an appreciable effect on the tumor microenvironment.

Each patient's tumor(s) will be biopsied before therapy and during therapy to assess the extent to which INCB024360 plus MELITAC 12.1 alters the tumor as evaluated by IHC and transcriptome analysis. In addition, the effect on immune responses in peripheral blood and on PBMC phenotype and character will be assessed (1) before therapy, (2) on day 21, before the first vaccine, (3) on day 42, a week after the third vaccine and coinciding with the day 42 biopsy, and (4) at week 16, 2 weeks after the sixth vaccine.

Therapeutic response will be assessed by serial scans and measures of circulating tumor cells. Overall clinical response rate and tumor progression will be assessed by evaluating nonbiopsied lesions if present, using standard methods (RECIST and irRC), including physical exam and CT scans performed before therapy, at weeks 8, 16, 26 and every 3 months through 1 year according to standard practice. If a clinical response is seen at week 8 a confirmatory scan is to be repeated at least 4 weeks later (week 12), therefore obtaining the week 16 scan may be delayed an additional 4 weeks and repeated at week 20. After week 26 scans are to be done every 12 weeks in patients without progression. Both systems will be used for reporting response. Patients may be managed in accordance with irRC guidelines as published by Wolchok [[Wolchok 2009](#)]. The irRC criteria allow for reporting as "response" patients that respond after a period of progression. The irRC criteria accordingly do not demand immediate cessation of experimental therapy with the first sign of progression.

In addition, the safety and tolerability of INCB024360 with MELITAC 12.1 will be assessed in this study utilizing the National Cancer Institute Common Terminology Criteria for Adverse Events v4.0 (NCI CTCAE v4.0).

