3. PATIENT SELECTION

3.1 Eligibility Criteria

- 3.1.1 Patients must have malignant melanoma validated by histology or cytology. Patients may have had primary cutaneous, mucosal, or ocular melanoma or metastasis from an unknown primary site.

NOTE: Patients must have measurable disease, defined as at least 1 lesion that can be accurately measured in at least 1 dimension (longest diameter to be recorded for non-nodal lesions and short axis for nodal lesions) as ≥ 20 mm with conventional chest x-ray or as ≥ 10 mm with spiral computed tomography (CT) scan, magnetic resonance imaging (MRI), or calipers by clinical exam. See [Section 11](#) for the evaluation of measurable disease.

- 3.1.2 Unresectable stage III or IV melanoma validated by clinical criteria (including recurrent melanoma), or patients with multiple skin/soft tissue metastases of melanoma that may be resectable but are judged to have a future recurrence risk exceeding 70% (e.g., large adenopathy, distant skin metastases or multiple in-transit melanoma metastases). Tumor deemed amenable to biopsy (excisional, incisional, or core, with at least 100 mm³ tumor volume per biopsy date) and fine-needle aspiration (FNA) biopsy.

Note: Optimally, patients will have tumor approachable for three serial biopsies during the trial. For patients with only one or two tumors approachable for biopsy, available tumor blocks from prior biopsies can serve as the pretreatment sample, but only if formalin-fixed tumor tissue is available and adequate to provide at least 20 unstained slides with sufficient tumor for analysis.

NOTE: Patients with unresectable advanced stage III or IV melanoma (including recurrent melanoma) are only eligible if they have failed at least one other first-line systemic therapy (other than adjuvant therapy). Exceptions to this requirement are those patients who have refused and/or are ineligible for other systemic therapies.

NOTE: BRAFi should be considered for all ‘unresectable’ or metastatic melanoma with BRAFV600E mutation; for low burden in-transit disease patients may enter trial without prior systemic therapy.

- 3.1.2.1 Stage IV no evidence of disease (NED) is excluded by this criterion

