9. BIOMARKER, CORRELATIVE, AND SPECIAL STUDIES

9.1 **Biomarker Studies**

9.1.1 **Collection of Specimens**

9.1.1.1 **Fine-Needle Aspiration (FNA) Biopsy of Tumor**

FNA biopsy will be prepared as detailed below and stored frozen in liquid nitrogen.

9.1.1.2 **Tumor Biopsies**

Biopsy specimens must include at least 100 mm³ of tumor tissue and ideally 1 cm³ or more. The specimens may be obtained by excisional biopsy, incisional biopsy, or core biopsy. Each surgical specimen or set of core biopsies will be divided into 5 portions: 1/4th will be placed in RPMI and will be processed to yield cryopreserved viable cells for flow cytometric analysis, 1/4th will be fixed in formalin and then embedded in paraffin for histology, 1/6th will be flash frozen in OCT for histology, 1/6th will be flash frozen without medium for Kyn/Trp ratio and 1/6th will be flash frozen in RNA Later for gene expression. (See Laboratory Manual for additional information).

If an archived pre-treatment biopsy is obtained from a formalin-fixed paraffin-embedded (FFPE) tissue block, there must be at least 20 slides available for study.

9.1.1.3 **Blood**

Blood will be collected for serum and PBMC isolation as designated below.

9.1.2 **Processing and Shipping of Specimen(s)**

Tumor specimens will be collected as described above, at the bedside when tumor is biopsied. They will then be processed and shipped as specified below.

9.1.2.1 **Portion for single-cell suspensions**

This will be submitted to mechanical dissociation then, as appropriate, enzymatic digestion (typically collagenase, DNAase, and hyaluronidase). The resulting cells will be collected by centrifugation and cryopreserved viably in 10% dimethyl sulfoxide (DMSO) and either 12.5% HSA (Human serum albumin or 12.5% FCS (Fetal calf serum) using a

controlled-rate freezer. Samples will be stored at -80°C and then batch-shipped on dry ice to the CITN Central Laboratory.

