Target lesions. All measurable lesions up to a maximum of 2 lesions per organ and 5 lesions in total, representative of all involved organs, should be identified as **target lesions** and recorded and measured at baseline. Target lesions should be selected on the basis of their size (lesions with the longest diameter), be representative of all involved organs, but in addition should be those that lend themselves to reproducible repeated measurements. It may be the case that, on occasion, the largest lesion does not lend itself to reproducible measurement in which circumstance the next largest lesion which can be measured reproducibly should be selected. A sum of the diameters (longest for non-nodal lesions, short axis for nodal lesions) for all target lesions will be calculated and reported as the baseline sum diameters. If lymph nodes are to be included in the sum, then only the short axis is added into the sum. The baseline sum diameters will be used as reference to further characterize any objective tumor regression in the measurable dimension of the disease.

Non-target lesions. All other lesions (or sites of disease) including any measurable lesions over and above the 5 target lesions should be identified as **non-target lesions** and should also be recorded at baseline. Measurements of these lesions are not required, but the presence, absence, or in rare cases unequivocal progression of each should be noted throughout follow-up.

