11.1.4 Response Criteria

11.1.4.1 Evaluation of Target Lesions by RECIST

Complete Response (CR): Disappearance of all target lesions. Any pathological lymph nodes (whether target or no-target) must have reduction in short axis to <10 mm.

Partial Response (PR): At least a 30% decrease in the sum of the diameters of target lesions, taking as reference the baseline sum diameters.

Progressive Disease (PD): At least a 20% increase in the sum of the diameters of target lesions, taking as reference the smallest sum on study (this includes the baseline sum if that is the smallest on study). In addition to the relative increase of 20%, the sum must also demonstrate an absolute increase of at least 5 mm. (**NOTE**: the appearance of one or more new lesions is also considered progressions).

Stable Disease (SD): Neither sufficient shrinkage to qualify for PR nor sufficient increase to qualify for PD, taking as reference the smallest sum diameters while on study.

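### The restriction of response reading to nonbiopsied lesions is not carried into the target-lesion, index-lesion or CR/PR rules, so an excisional or roughly 1 cm³ biopsy can be scored as a response in some patients

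*Combined protocol and SAP*

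**What the plan says.** Section 11 states the intention: overall response and progression are to be assessed by "evaluating nonbiopsied lesions if present", using both RECIST and irRC.

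The detailed rules do not mention biopsy:

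- **RECIST target lesions (11.1.2).** The pool is "All measurable lesions up to a maximum of 2 lesions per organ and 5 lesions in total". The selection rule is "Target lesions should be selected on the basis of their size (lesions with the longest diameter", qualified by organ representation and by a preference for lesions that "lend themselves to reproducible repeated measurements".
- **RECIST response (11.1.4.1).** CR is "Disappearance of all target lesions" and PR is "At least a 30% decrease in the sum of the diameters of target lesions". Neither considers why a lesion shrank or vanished.
- **irRC (11.1.4.3).** Index lesions, irCR and irPR are defined without reference to biopsied lesions.

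On the biopsies, Section 9.1.1.2 sets a minimum of 100 mm³ of tumor, ideally 1 cm³ or more, and adds: "The specimens may be obtained by excisional biopsy, incisional biopsy, or core biopsy". Section 3.1.1 requires only one measurable lesion. A note in 3.1.2 provides for limited access ("For patients with only one or two tumors approachable for biopsy") by allowing an archived block as the pretreatment sample.

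Section 13.6.2 keeps all eligible patients in the main response-rate analysis. Section 11.1.7 plans no review of response.

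**The concern.** Section 11 recognizes that a biopsied lesion is a poor measure of drug effect, but the rules applied at the scan do not act on this. Two situations are left open. In the first, the patient has no nonbiopsied measurable lesion, and no section says how to score response. In the second, nonbiopsied lesions exist, but an investigator working from 11.1.2 alone picks the largest lesion, which may also be the one sampled.

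The timing allows the error. The day 21 biopsy is mandatory (5.1), and the day 42 biopsy, where done, also precedes the week 8 scan. The pretreatment biopsy may be taken in the 14 days before treatment, whereas baseline imaging may be up to 4 weeks before it (11.1.3), so the scan can come first.

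Little in the plan would detect the error. A confirmatory scan at least 4 weeks later finds an excised lesion still absent, and there is neither a response review nor a control arm. At stake is the credibility of a small, uncontrolled response rate. Section 5.1 also makes response at 3 months a ground for considering additional INCB024360.

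**Working it through.** The documents give no power or error rate for response, so there is no planned figure to reproduce. The check applies the protocol's own thresholds.

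**Inputs.** PR is a 30% fall in the sum of diameters (11.1.4.1). irPR is a 50% fall in the sum of products of diameters, SPD (11.1.4.3). A biopsy takes 100 mm³ at minimum and ideally 1 cm³ or more (9.1.1.2). The minimum measurable non-nodal lesion on CT or by calipers is 10 mm (3.1.1). N = 12 (13.3).

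**Step 1: whole-lesion excision, other lesions unchanged.** If m of k equal lesions are excised, both the RECIST sum and the SPD fall by m/k.

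| Excised | Fall | RECIST | irRC |
|---|---|---|---|
| 1 of 1 | 100% | CR if no other disease | irCR if no other disease |
| 1 of 2 | 50% | PR | irPR |
| 1 of 3 | 33.3% | PR | irSD |
| 1 of 4 | 25% | SD | irSD |
| 1 of 5 | 20% | SD | irSD |
| 2 of 5 | 40% | PR | irSD |

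With unequal lesions the largest weighs more. Excising the 20 mm lesion from 20/15/10 mm gives 20/45 = 44.4% for RECIST. For SPD, taking the two perpendicular diameters as equal, it gives 400/725 = 55.2%.

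**Step 2: partial sampling of a single target lesion.** Assume a sphere, V = πd³/6, with the remainder again spherical. A 30% smaller diameter leaves 0.7³ = 0.343 of the volume, so 65.7% must be removed. The largest lesion that reaches PR after removal of R mm³ is d = [6R/(0.657π)]^(1/3).

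- R = 300 (three minimum samples): d = 9.6 mm, below the 10 mm minimum. In a 10 mm lesion (524 mm³), (224/524)^(1/3) = 0.753, a fall of 24.7%. The SPD falls by 1 − 0.753² = 43.3%. Neither threshold is met.
- R = 1000 (one 1 cm³ sample): d = 14.3 mm. A 13 mm lesion falls by 49.3%, a 15 mm lesion by 24.3%.
- R = 3000 (three 1 cm³ samples): d = 20.6 mm.

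**Step 3: effect on the response rate.** One false responder adds 1/12 = 8.3 points. With no true responders, the rate and its exact 95% interval are:

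| False responders | Rate | 95% CI |
|---|---|---|
| 0 | 0% | 0 to 26.5% |
| 1 | 8.3% | 0.2 to 38.5% |
| 2 | 16.7% | 2.1 to 48.4% |

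**Step 4: time to progression.** RECIST progression is a rise of at least 20% and at least 5 mm from the smallest sum on study. In the 20/15/10 mm case the sum of 45 mm must rise by 9 mm. After excision of the 20 mm lesion the sum is 25 mm, and a 5 mm rise suffices. Growth in the remaining lesions therefore triggers progression sooner, while growth of the excised lesion can no longer be seen. The net direction is not fixed.

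**The case against.** The strongest reply is that Section 11 already contains the safeguard. Its sentence covers both RECIST and irRC. It can be read as setting the pool of lesions within which 11.1.2 and 11.1.4.3 then select, and nothing in the protocol ranks 11.1.2 above it. The preference for reproducibly measurable lesions also points away from one due for excision. This stands for patients who have nonbiopsied measurable lesions: the sections read together protect them, and what is missing is the cross-reference. It does not help a patient who has none.

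Such patients may be few. Having one or two tumors accessible for biopsy does not mean having only one or two measurable lesions, and eligibility otherwise asks for unresectable disease or multiple metastases. A false CR also needs all non-target disease to be gone. An archived block can replace the pretreatment biopsy, the week 6 biopsy is optional under 2.4.4 and the calendar, and a core need not shorten the longest diameter. All of this limits the frequency, which the documents do not give, but none of it supplies the missing rule.

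A reader might infer that any protocol biopsy of a measured lesion can produce a response, or that the bias always flatters the drug, including by delaying progression. The documents support neither. Minimum samples stay below the thresholds (Step 2), and time to progression can move either way (Step 4).

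**Conclusion.** The concern holds in a limited form. Where all measurable disease is biopsied, or where 11.1.2 is applied by size alone, the rules as written allow an excisional or roughly 1 cm³ biopsy to be scored as PR or CR. The excision results for the RECIST sum need no shape assumption, only that the other lesions are unchanged. The partial-sampling limits (14.3 mm for one 1 cm³ sample, 20.6 mm for three) rest on the spherical model and a single target lesion. With four or five equal targets, excising one does not reach PR.

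Each case adds 8.3 points to the response rate. The counts of one and two false responders are illustrative.

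It would go too far to say that the trial's main result is compromised. Response rate and time to progression are secondary and described as preliminary data (1.2, 13.5.5), and the CD8+ primary endpoint does not depend on target-lesion selection. The change is worth making because the gap is real, the plan would not detect the error, and the remedy is short.

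**What to change.** In 11.1.2 and 11.1.4.3, state two rules:

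1. A lesion biopsied or planned for biopsy may not be a target or index lesion when another measurable lesion exists.
2. Disappearance or shrinkage of a lesion through biopsy does not count toward CR, PR, irCR or irPR.

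For patients with no nonbiopsied measurable lesion, add that CR or PR is not assigned. They count as non-responders in the all-eligible denominator and are listed separately as not assessable for response. Progression is still recorded when new lesions or unequivocal growth are seen.

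Placing these patients in category 9 of 13.6.2 without comment would not be enough. That section treats categories 4 to 9 as treatment failure and equates failure with disease progression, so stable patients would be labeled as progressed. A short exception there avoids this.

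The cost is a few sentences. The response rate may be slightly lower, and a true response in a patient with only biopsied disease cannot be credited.
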